13.2. Sample Size/Accrual Rate

We plan to accrue 21 eligible patients. The expected monthly accrual rate is 1-2 patients. Thus, accrual is anticipated to take approximately 2 years.

13.3. Stratification Factors

No stratification factors are pre-defined within the protocol

13.4. Reporting and Exclusions

- 13.4.1 Evaluation of toxicity: All patients will be evaluable for toxicity from the time of their first treatment with pembrolizumab
- 13.4.2 Evaluation of response: All patients included in the study must be assessed for response to treatment, even if there are major protocol treatment deviations or if they are ineligible. Each patient will be assigned one of the following categories: 1) complete response, 2) partial response, 3) stable disease, 4) progressive disease, 5) early death from malignant disease, 6) early death from toxicity, 7) early death because of other cause, or 9) unknown (not assessable, insufficient data). [Note: By arbitrary convention, category 9 usually designates the "unknown" status of any type of data in a clinical database.]

All of the patients who met the eligibility criteria (with the possible exception of those who received no study medication) should be included in the main analysis of the response rate. Patients in response categories 4-9 should be considered to have a treatment failure (disease progression). Thus, an incorrect treatment schedule or drug administration does not result in exclusion from the analysis of the response rate. Precise definitions for categories 4-9 will be protocol specific.

14.0 Data and Safety Monitoring Plan

14.1. Monitoring Plan

FCCC ISRU will monitor the medical and study records of each participant accrued throughout the course of the study. In addition, the ISRU will collect and report data to the study Sponsor Investigator who will review these data on a regular basis at a rate dependent on subject accrual. All serious adverse events (SAEs) will be reviewed on a real time basis first by the study site PI and subsequently by the ISRU and Sponsor Investigator as applicable.

14.2. Data Safety Monitoring Board

Interim analysis of toxicity, outcome and ongoing scientific investigations may be performed at least every 3 months by the Fox Chase Cancer Center Data Safety Monitoring Committee (FCCCDSMB). In this capacity the FCCCDSMB will serve as an advisory committee to the Sponsor Investigator. The FCCCDSMB will review those aspects of this trial that are outlined in the responsibilities section of the Data and Safety Monitoring Plan (DSMP). If the committee decides that changes should be made to this trial, it will make recommendations in writing to the Sponsor Investigator, the Associate Director of Clinical Research, and the Protocol Management Executive Committee, which, in turn, have the authority to approve or disapprove these recommendations. These changes will be discussed with the Sponsor Investigator before they are implemented. These changes may include early termination of accrual. Other changes might include altering the accrual goals or changing the eligibility criteria for the trial.

15.0 Administrative

This study will be conducted in accordance will local, state and Federal regulations and according to accepted good clinical practice guidelines.

15.1. Data Reporting

The FCCC Study Monitor will request eCRF to be completed within 2 weeks of the protocol visit. Participating sites are responsible to respond to queries prior to the next scheduled monitoring visit

The ISRU is responsible for compiling and submitting data to the Sponsor Investigator and statistician on an ongoing basis for monitoring as described in the data safety monitoring plan and reporting to the Data and Safety Monitoring Board.

All patient information will be stored in an EDC system accessible only to the study team members for the purpose of entering, reviewing and analyzing data. Any paper records, such as case report files, produced will be stored in a secure location.

The ISRU is responsible for distributing and tracking review of all IND Action Letters, Safety Reports, study specific Serious Adverse Events.

15.2. Retention of Records

In all cases the Study Monitor must be notified of any plans to move records to an offsite location prior to doing so.

15.3. Informed Consent

The IRB approved informed consent documents must be signed by the patient, or the patient's legally authorized representative, before his or her participation in the study. The case history for each patient shall document that informed consent was obtained prior to participation in the study. A copy of the informed consent documents must be provided to

the patient or the patient's legally authorized representative. If applicable, they will be provided in a certified translation of the local language.

Original signed consent forms must be filed in each patient's study file or medical record with a copy in the study file.

17.0 Appendices

17.1. ECOG Performance Status

Grade	Description						
0	Normal activity. Fully active, able to carry on all pre-disease						
0	performance without restriction.						
	Symptoms, but ambulatory. Restricted in physically strenuous						
1	activity, but ambulatory and able to carry out work of a light or						
	sedentary nature (e.g., light housework, office work).						
	In bed <50% of the time. Ambulatory and capable of all self-care, but						
2	unable to carry out any work activities. Up and about more than 50%						
	of waking hours.						
3	In bed >50% of the time. Capable of only limited self-care, confined						
5	to bed or chair more than 50% of waking hours.						
4	100% bedridden. Completely disabled. Cannot carry on any self-care.						
-	Totally confined to bed or chair.						
5	Dead.						
	n. J. Clin. Oncol.: Oken, M.M., Creech, R.H., Tormey, D.C., Horton, J., Davis, T.E.,						
	arbone, P.P.: Toxicity And Response Criteria Of The Eastern Cooperative Oncology						
Group. Am J Clin Oncol 5:649-655, 1982. The Eastern Cooperative Oncology Group, Robert Comis M.D., Group Chair.							

17.2. Collection, Shipment, and Processing of Blood Samples and Tissue for Correlative studies

Optional blood collection and storage of leftover tumor tissue sample for future exploratory research will be done only after obtaining informed consent from patients for future unspecified biomedical research. This consent will be a part of the informed consent process at the time of study entry.

Blood Sample Collection:

Three peripheral blood samples (up to 60 ml each) will be serially collected from each patient at the following time points:

- 1. Immediately prior to the first treatment, for a baseline assessment.
- 2. Immediately prior to the third treatment, which would occur at cycle 3.
- 3. When disease progression is observed, either during or post-treatment.

Instructions for Collection, Processing and Shipping Procedures for Blood and Tissue Specimens

Blood will be drawn by a physician, registered nurse or licensed phlebotomist prior to receiving the Pembrolizumab at the predefined time points. For correlative studies, blood will be drawn into **two (2) sodium heparin green top tubes** (about 20 ml) at the three time points. Also, one (1) red top tube and one (1) EDTA tube for cell free plasma (20 ml) will be drawn before cycle 1, every other assessment, and at the end of treatment for future research.

All blood samples for PBMC preparation will be processed in the Protocol Support Laboratory. Flow cytometry processing and analysis will be performed in the [name] laboratory on an Aria II flow cytometer (BD). Compensation (parallel controls using cells singly stained for each color) and data analysis will be performed using FlowJo flow cytometry analysis software (TreeStar). The percentage and/or mean fluorescence intensity (MFI) of cells staining for individual markers will be determined, and CD107A+ degranulating NK cells in functional assays, will be compared to isotype controls to establish baseline values. Pembrolizumab will be used to stain for PD-1 expression on leukocytes in pre-treatment samples and a secondary anti-human IgG4 will be used to assess the remaining Pembrolizumab bound to PD-1 on treatment samples. Samples should be collected according to the institutional procedures for venipuncture.

Archival tissue or biopsy - Tissue will be used for immunohistochemistry and next gene sequencing. If archival tissue is not available an optional biopsy may be performed. " Label slides with patient study #, pathology accession #. Slides will be prepared by PSL stored at 4°C, batched and transferred to Qualtek for immunohistochemistry analysis.

PBMC preparation (green top tubes) –

Remaining PBMC will be frozen in 10%DMSO + 90% FBS at a conc. of 5-10 x 10^6 cells/vial and stored at -70° C and transferred to liquid nitrogen.

17.3. Management of immune related adverse events from Pembrolizumab.

PDF provided separately

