3.3. Exploratory objectives

- To correlate biomarkers related to PD-1 blockade in tumor samples (such as TILs, PD-1, PD-L1) with overall response rate, progression free survival, and overall survival
- To characterize molecular and biological profile of tumors that respond to pembrolizumab by performing genomic analysis of tumor samples and by evaluating the expression levels of PD-L1, PD-L2 on tumor cells; PD-L1, PD-1 on TILs and T-regulatory cells (T-regs) in the tumor microenvironment. To compare PD-1 expression and leukocyte activation markers on circulating T-regs pre-treatment, at week 6, and at time of disease progression
- To compare functional responses (degranulation) by NK cells pre-treatment, at week 6, and at end of treatment.

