4.5. Rationale for Dose Selection/Regimen/Modification

Previously, an open-label Phase I trial (NCT01848834) was conducted to evaluate the safety and clinical activity of single agent Pembrolizumab (MK-3475). The dose escalation portion of the trial evaluated three dose levels, 1 mg/kg, 3 mg/kg, and 10 mg/kg, administered every 2 weeks (Q2W) in subjects with advanced solid tumors. All three dose levels were well tolerated and no dose-limiting toxicities were observed. This first in human study of pembrolizumab showed evidence of target engagement and objective evidence of tumor size reduction at all dose levels (1 mg/kg, 3 mg/kg and 10 mg/kg Q2W). No MTD has been identified to date. Recent data from other clinical studies within the pembrolizumab program has shown that a lower dose of pembrolizumab and a less frequent schedule may be sufficient for target engagement and clinical activity.

PK data analysis of pembrolizumab administered Q2W and Q3W showed slow systemic clearance, limited volume of distribution, and a long half-life (refer to IB). Pharmacodynamic data (IL-2 release assay) suggested that peripheral target engagement is durable (>21 days). This early PK and pharmacodynamic data provides scientific rationale for testing a Q2W and Q3W dosing schedule.

A population pharmacokinetic analysis has been performed using serum concentration time data from 476 patients. Within the resulting population PK model, clearance and volume parameters of pembrolizumab were found to be dependent on body weight. The relationship between clearance and body weight, with an allometric exponent of 0.59, is within the range observed for other antibodies and would support both body weight normalized dosing or a fixed dose across all body weights. Pembrolizumab has been found to have a wide therapeutic range based on the melanoma indication. The differences in exposure for a 200 mg fixed dose regimen relative to a 2 mg/kg Q3W body weight based regimen are anticipated to remain well within the established exposure margins of 0.5 - 5.0 for pembrolizumab in the melanoma at 10 mg/kg Q3W vs. the proposed dose regimen of 2 mg/kg Q3W (i.e. 5-fold higher dose and exposure). The population PK evaluation revealed that there was no significant impact of tumor burden on exposure. In addition, exposure was similar between the NSCLC and melanoma indications. Therefore, there are no anticipated changes in exposure between different indication settings.

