Adverse events will be assessed continuously throughout the study. If 6 of the first 12 patients have to discontinue study treatment due to treatment related adverse events the study will be interrupted for consideration of dose reduction or termination. If ever 8 of the 21 eligible patients have to discontinue study treatment due to treatment related adverse events the study will be suspended and early termination for excess toxicity will be considered after careful investigation of the causes of the higher than expected toxicities. Once the root of the higher than anticipated toxicities has been determined, the study team will confer with the FCCC DSMC and IRB to make a determination whether accrual can be resumed or the study will be terminated early. The chance of early termination with a true toxicity of 50% is 61%. The chance of study termination under the null of 20% true toxicity is 2.7% and is 83% if true toxicity is 50%.

As discussed earlier, no second line therapies have been prospectively evaluated in high grade neuroendocrine carcinomas and small retrospective studies have shown dismal results with chemotherapy [11-13]. Hence we decided to proceed without a definite stopping rule for futility, given minimal if any, harm associated with ineffective therapy to study participants.]

Correlative studies: Due to this limited sample size, all exploratory analyses of associations of biomarkers with outcomes and changes in marker levels pre- and during treatment will be largely descriptive in nature.

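### PD-1 on circulating T-regs is read as drug-accessible receptor before treatment but as drug-bound receptor on treatment, so a change from baseline partly reflects drug exposure

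*Combined protocol and SAP*

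**What the plan says.** The exploratory objective in Section 3.3 is "To compare PD-1 expression and leukocyte activation markers on circulating T-regs pre-treatment, at week 6, and at time of disease progression". Section 4.7 adds that PD-1 expression before treatment, during it and at progression will be examined for association with response and outcome.

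The method is in Section 17.2. Before treatment: "Pembrolizumab will be used to stain for PD-1 expression on leukocytes in pre-treatment samples". For later samples: "a secondary anti-human IgG4 will be used to assess the remaining Pembrolizumab bound to PD-1 on treatment samples". The readout is the same in form throughout: "The percentage and/or mean fluorescence intensity (MFI) of cells staining for individual markers will be determined".

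The second sample is taken "Immediately prior to the third treatment, which would occur at cycle 3", and the third "When disease progression is observed, either during or post-treatment". Section 13.1 says that associations with outcome and "changes in marker levels pre- and during treatment will be largely descriptive in nature".

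The documents describe no measurement of total PD-1 on treatment, no correction for occupancy and no bridging between the two stains. Section 17.2 also does not say which stain applies to a progression sample drawn after treatment has ended.

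**The concern.** Before the first dose no drug is on the cells, so added pembrolizumab can label every PD-1 molecule it can reach. On treatment, the stain described detects only drug that is already there. The first reading is an amount of receptor; the second is an amount of receptor multiplied by the fraction occupied. Section 3.3 gives both the same name and sets them side by side.

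A fall from baseline could then mean less PD-1, less bound drug, or both. A true rise could be hidden. In the progression sample, the occupied fraction depends on how long ago the last dose was given. That interval depends in turn on why the patient stopped, so the artefact could line up with clinical course, which is what Section 4.7 wants PD-1 to be related to.

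**Working it through.** The documents state no figure for this comparison, so there is nothing to reproduce. The check sets the two readings side by side and then illustrates the effect.

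**Inputs**

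- Pre-treatment stain: added pembrolizumab (Section 17.2). That this captures all drug-accessible PD-1 is an inference from the absence of drug before dose 1.
- On-treatment stain: anti-IgG4 against drug still bound (Section 17.2).
- Time 2: just before dose 3. With 21-day cycles this is 2 × 21 = 42 days after dose 1 and about 21 days after dose 2, a trough.
- Time 3: at progression, on or off drug (Section 17.2).
- Occupancy q: not stated. Section 4.5 says only that peripheral engagement lasts more than 21 days, from an IL-2 release assay. Values of q from 50% to 100% are assumed below.

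**Model for fluorescence intensity**

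Let T0 and T1 be true PD-1 before and on treatment, and k0 and k1 the staining efficiencies. With a signal linear in bound drug:

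- baseline signal = k0 × T0
- on-treatment signal = k1 × T1 × q
- apparent change = (k1/k0) × (T1/T0) × q − 1

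With equal efficiencies (k1 = k0) this becomes (T1/T0) × q − 1. For unchanged PD-1 and q = 0.9, it is 1 × 0.9 − 1 = −10%. For a true 1.5-fold rise and q = 0.7, it is 1.5 × 0.7 − 1 = +5%.

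| True T1/T0 | q = 100% | 90% | 80% | 70% | 50% |
|---|---|---|---|---|---|
| 1.0 | 0% | −10% | −20% | −30% | −50% |
| 1.5 | +50% | +35% | +20% | +5% | −25% |
| 2.0 | +100% | +80% | +60% | +40% | 0% |

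The true change is recovered only in the q = 100% column, and only if k1 = k0.

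**Percentage positive**

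Section 17.2 also allows the percentage of staining cells as the readout. A partly occupied cell can still count as positive, so the percentage need not fall in proportion to q. The table does not apply to it.

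**Where q is likely to differ**

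- At week 6 every patient is sampled at a similar interval after dose 2. Durable engagement suggests q may be high and the bias small.
- At progression, a patient who progresses on drug is sampled near a dose. A patient who stopped after a complete response (Section 6.7), after 35 cycles or for toxicity (Section 6.6) is then scanned every 9 weeks, and every 12 weeks after a year (Section 8.5.3). That patient may be sampled well after the last dose. As drug clears, the bound-drug signal falls whatever PD-1 does.

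**The case against.** The strongest reply is that Section 17.2 already keeps the two quantities apart. It uses the term expression only for pre-treatment samples and describes the later reading as remaining bound drug. No change score is defined anywhere, and Section 13.1 makes the work largely descriptive. That is fair as far as it goes, but Sections 3.3 and 4.7 still call all three readings PD-1 expression and plan to compare them or relate them to outcome. Describing two different quantities does not make them comparable.

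Anti-IgG4 might also be the detection step for the pre-treatment stain. That would harmonise detection but not the quantity: on-treatment cells would still show only drug bound in the patient.

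Section 17.2 is a collection and processing appendix, and a laboratory procedure may contain a total-PD-1 tube that it does not mention. This cannot be excluded. The point is that the plan does not provide for one.

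Three further objections stand and limit the point:

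- A reader might infer that the week-6 comparison is uninterpretable. The documents do not show that. Their only evidence on engagement points to a smaller bias at that time.
- A reader might take the whole progression time point to be confounded by washout. Progression is itself a reason to stop treatment (Section 6.6), and the calendar grid in Section 10.1 marks correlative blood at end of treatment but not at follow-up visits. The washout problem concerns patients who stop for another reason and progress later.
- Section 4.5 describes slow clearance and a long half-life, so loss of bound drug after stopping may be gradual.

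**Conclusion.** The point holds as a mismatch between objective and assay. As written, the plan compares drug-accessible PD-1 at baseline with drug-bound PD-1 afterwards, and these agree only with complete occupancy and equally efficient stains.

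The size of the bias cannot be derived from the documents. The 10%, 30% and 50% figures are illustrations for fluorescence intensity under assumed occupancy, a linear signal and equal efficiency. A reader might take them as estimates of the bias in this trial, but nothing in the documents supports a particular occupancy.

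The consequence is minor. It concerns one marker in one exploratory objective, together with the use that Section 4.7 makes of the later readings. Response rate, PFS, OS, safety, sample size, associations using baseline PD-1 alone, the other leukocyte activation markers and the NK degranulation assay do not depend on this switch of stain.

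**What to change.** In Sections 3.3, 4.7 and 17.2, name the on-treatment anti-IgG4 reading as drug-bound PD-1 (an occupancy reading) and do not compare it with baseline as PD-1 expression. State which stain applies to a progression sample taken after treatment has ended. Record the time since last dose for every progression sample and report it beside the result. This needs only a change of wording and one derived date interval; it adds no laboratory work.

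If cell yield allows, also stain one aliquot at every time point with saturating pembrolizumab followed by anti-IgG4, and make the comparison over time on that total. On treatment, the unsaturated reading divided by the saturated one would then estimate occupancy directly. The cost is one more staining tube from a limited sample: about 20 ml of blood per time point also has to serve the other flow markers and the NK assay. Section 17.2 expects leftover cells to be frozen but gives no yield, so the laboratory should confirm feasibility before the tube is made mandatory.

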17.4. Common Terminology Criteria for Adverse Events V4.0 (CTCAE)

The descriptions and grading scales found in the revised NCI Common Terminology Criteria for Adverse Events (CTCAE) version 4.0 will be utilized for adverse event reporting. (http://ctep.cancer.gov/reporting/ctc.html)
